6 ELEGIBILITY

6.1 INCLUSION CRITERIA:

Participants must meet all of the following inclusion criteria to be eligible to register for this trial: older than 75 years old diagnosed of frailty, according to Fried's Criteria, if is not possible to use the Fried Scale, FRAIL Scale will be used.

6.2 EXCLUSION CRITERIA:

- Do not able to give informed consent.
- Participants with moderate-severe cognitive impairment according to MMSE scale (score 18 or lower) and/or the GDS scale (score 5 or higher)*.
- Those with physical disability according to Barthel Index (lower to 40)
- Participants with critical acute disease who might need admission in an Intensive Care Unit (ICU).
- Life expectancy lower than six months
- Nursing home residents

* This cut-off was selected to establish a higher sensitivity and maintain a good recruitment rate.(24)

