11. APPENDIX

APPENDIX 2

FRIED'S CRITERIA

1- **Weight loss:**

We have to ask the patient if he or she has lost weight unintentionally in the past year, and if the loss was greater than 4,5 kg (10 lb).

- YES (1)
- NO (0)

2- **Exhaustion:**

- "I felt that everything I did was an effort during the past week"
- I could not get "going"

If SOME (OR BOTH) answers are YES, one point for frailty will be counted.

3- **Physical activity:**

Does the patient perform less than or equal to the physical activity indicated weekly?

Men: < 383 kcal / week (walking \leq 2 hours and 30 minutes / week)

Women: < 270 kcal / week (walking \leq 2 hours / week)

We ask the patient to respond with YES or NO if he/she performs these activities.

If they answer YES, one point for frailty will be counted.

4- **Slowness:** measured as the time it takes for the patient to travel 15 feet to their usual walking speed.

SEX	Height(CM)	CUT OFF
MEN	\leq 173 cm	\geq 7s
	$>$ 173 cm	\geq 6s
WOMEN	\leq 159 cm	\geq 7s
	$>$ 159 cm	\geq 6s

This is done as follows: we will indicate to the patient to stand immediately behind the starting line, we will tell him/her to start walking "as he/she usually does". The patient is then stopped. We will do the test twice and we will take the best score of the two. The time will be recorded in seconds.

5- **Weakness:** Assessed by grip strength.

BMI♂	CUT-OFF	BMI♀	CUT-OFF
\leq 24	<29kg	\leq 23	<17kg
24,1-26	<30kg	23,1-26	<17,3kg
26,1-28	<30kg	26,1-29	<18kg
> 28	<32kg	>29	<21 kg

He/she will rest for about 30 seconds, and he/she will repeat the exercise two more times. We will record the best of all results.

FRAIL

- 1.- **Fatigue** is measured by asking respondents how much time during the past 4 weeks they have felt tired with responses of “all of the time” or “most of the time” scored as 1 point.
- 2.- **Resistance** is assessed by asking participants if they have had any difficulty walking up 10 steps alone without resting and without aids.
- 3.- **Ambulation** is assessed by asking if they had any difficulty walking several hundred meters alone and without aids: a yes response is scored as 1 point.
- 4.- **Illness** is scored 1 for respondents who report 5 or more illnesses out of 11 total illnesses:(hypertension, diabetes, cancer (other than a minor skin cancer), chronic lung disease, heart attack, congestive heart failure, angina, asthma, arthritis, stroke, and kidney disease).

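### Fried item 3 (physical activity) in Appendix 2 is worded in two conflicting directions, and one of them gives the frailty point to active patients

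*Combined protocol and SAP*

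**What the plan says.** Section 6.1 requires patients to be "diagnosed of frailty, according to Fried's Criteria, if is not possible to use the Fried Scale, FRAIL Scale will be used". The scoring is printed in Appendix 2. Fried item 3 has four parts:

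- a lead question: "Does the patient perform less than or equal to the physical activity indicated weekly";
- limits by sex, with a strict inequality for kcal per week (under 383 for men, under 270 for women) and a non-strict one for walking (up to 2 h 30 min for men, up to 2 h for women);
- an operating instruction: "We ask the patient to respond with YES or NO if he/she performs these activities";
- a scoring rule: "If they answer YES, one point for frailty will be counted".

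Section 7.2 places 1:1 allocation through the eCRF after eligibility has been verified. Section 9.2 repeats a frailty assessment at discharge with Fried and/or FRAIL. Table 2 marks both scales at the initial visit.

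**The concern.** The lead question and the operating instruction can point in opposite directions, yet one scoring rule serves both. Under the lead question, YES identifies the inactive patient, which is the direction a frailty point needs. If the operating sentence is what the patient hears, someone who walks well beyond the limit naturally says YES and scores, while someone who hardly walks says NO and does not.

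Frailty defines the trial population. Section 5 plans recruitment at six centres in three countries, and section 7.4 evaluates the intervention by clinical setting. If assessors differ in how they ask this item, patients near the qualifying score could be admitted at one centre and refused at another. The discharge Fried score would carry the same ambiguity, though frailty is not among the outcomes listed in section 4.

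**Working it through.** The plan states no figure on this point, so there is none to reproduce. The check sets the two wordings side by side and then asks when the difference matters.

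**Direction of the item**

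| Patient | Lead question | Operating sentence taken literally |
|---|---|---|
| Inactive (at or below the limit) | YES, 1 point | NO, 0 points |
| Active (above the limit) | NO, 0 points | YES, 1 point |

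The two readings differ by exactly one point for every patient.

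**When one point changes eligibility.** Let t be the qualifying total. The documents do not give it, so the full range is shown. Status changes only if the other four items total t − 1, which happens in C(4, t − 1) patterns of those items. Each pattern occurs once with an active and once with an inactive patient, so 2 × C(4, t − 1) of the 32 response patterns are affected.

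| t | C(4, t − 1) | Patterns that change status, of 32 |
|---|---|---|
| 1 | 1 | 2 |
| 2 | 4 | 8 |
| 3 | 6 | 12 |
| 4 | 4 | 8 |
| 5 | 1 | 2 |

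**Share of patients.** Assumptions, none of them from the documents: t = 3; the other four items are independent, each positive with probability p between 0.3 and 0.5; the operator reverses the item for every patient. Then

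P(exactly 2 of the other 4) = 6 p²(1 − p)²

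- p = 0.3: 6 × 0.09 × 0.49 = 0.265
- p = 0.4: 6 × 0.16 × 0.36 = 0.346
- p = 0.5: 6 × 0.25 × 0.25 = 0.375

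So 26-38% of patients assessed with Fried by such an operator would change status.

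**Split by direction.** Assume further that 50-70% of those screened are truly inactive, independently of the other items.

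- Wrongly included (active): from 0.265 × 0.3 = 8% to 0.375 × 0.5 = 19%.
- Wrongly rejected (inactive): from 0.265 × 0.5 = 13% to 0.375 × 0.7 = 26%.

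**Across the trial.** If a fraction r of Fried assessments is done the reversed way, the share affected is r × 26-38%. The documents say nothing about r, so the lower end is 0%. Patients qualified on FRAIL are untouched, because that scale has no weekly-activity item of this kind.

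**The case against.** The strongest reply is that the item reads correctly in sequence. The activities in the operating sentence are those listed just above it, with upper limits, under a question about doing that amount or less. On that reading YES means low activity throughout and the sentence is merely loose. A man who walks exactly 2 h 30 min is within the printed limit and should score, so he is no example of reversal. The document also contains Spanish residue (section 9.4 repeats its FRAIL line in Spanish), so the sentence may be a translation slip. The local-language forms and eCRF screens are not available to check.

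Much of this stands: reversal is one reading, and its frequency is unknown. What survives is that the sentence telling staff what to ask the patient is the one that can reverse the answer, and nothing elsewhere in the documents corrects it.

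A reader might infer more than the text supports:

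- **That eligibility in general depends on the operator.** Only patients one point from the total are affected, and only when Fried is used. Section 6.1 provides a second route: "if is not possible to use the Fried Scale, FRAIL Scale will be used".
- **That the trial has no usable frailty definition because neither scale prints a qualifying total.** No total is printed, although section 6.2 gives numerical cut-offs for its MMSE, GDS and Barthel exclusions. But both instruments are named, and trained geriatric teams would take totals from them. The missing point for FRAIL item 2, which "is assessed by asking participants if they have had any difficulty walking up 10 steps alone without resting and without aids", and the missing points for Fried items 4 and 5 are gaps of the same kind.
- **That effects by setting cannot be compared, or that the arms are biased.** Inconsistent entry may blur comparisons between settings but does not rule them out. Eligibility precedes 1:1 allocation, so misclassification favours neither arm.

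**Conclusion.** The point holds as a conflict of wording in one item of the main eligibility instrument. Taken literally, the operating sentence of Fried item 3 awards the frailty point to active patients and denies it to inactive ones; taken with the lead question, it does not. The 26-38% is conditional on Fried being used, a qualifying total of 3, independent items at 30-50% prevalence, and an operator who fully reverses the question. It is not an estimate for the trial. The consequence is confined to who is enrolled and to consistency of enrolment between centres. The unprinted totals and point values are missing detail, not a failure of the entry criterion.

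**What to change.** Reword the operating sentence of Fried item 3, or remove it, so that it agrees with the lead question and YES can only mean this amount of activity or less. Make the kcal and walking limits consistent, since one is now strict and the other is not. Check that the eCRF and every local-language form carry the same wording.

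As housekeeping, the sponsor should print its own qualifying total for each scale, add the missing point values (FRAIL item 2, Fried items 4 and 5), and record which scale qualified each patient. No total is proposed here, because the documents give none.

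The cost is an edit to the appendix and the matching form text, one recorded field, and a short note to sites. No assessment is added, as Table 2 already marks both scales at the initial visit.

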4 OUTCOMES

4.1 PRIMARY OUTCOMES:

1. **Disability:** It was measured by the Barthel Index for basic Activities of Daily Living and the Lawton index for instrumental activities of daily living.
2. **Functional status and performance-based measures:** Functional status and performance-based measures: Is measured by Short Physical Performance Battery (SPPB), Physical Activity Scale for the Elderly (PASE SCALE).
3. **Quality of Life:** Quality of life was assessed by self-reported questionnaire EuroQL 5D 5L. It will be measured during admission to hospital and follow-up.
4. **Geriatrician Intervention:** The impact of their intervention is measured by quantifying in a register any additional tests requested and medical advice by other specialists.

4.2 SECONDARY OUTCOMES:

Prevalence of Delirium: The delirium cases are detected by Confusion Assessment Method (CAM) scale.

Cognitive Impairment: Will be measured by the Mini Mental State Examination (MMSE) in the initial assessment.

Depression: will be assessed using the Geriatric Depression Scale in the baseline assessment.

Health-care associated infections: Acquired during hospitalization start.

Geriatric Syndromes: The geriatric evaluation including the following aspects: clinical, functional, mental and social.

Comorbidity: Will measured at initial assessment thorough Charlson index

Nutritional Status: Will measured at initial assessment thorough the Mini Nutritional Assessment and body Mass index.

Polypharmacy: Defined as five or more prescription drugs.

Mortality rate: Number of deaths during follow-up. It is calculated using official report of the National Statistics Institute (INE).

Average stay hospitalization: Average length of stay of stay all discharges. We will obtain from Hospital Admissions service.

Hospitalization Rate in Emergency room: Number of hospital admissions over the total of patients admitted in the hospital.

Readmission rates: Number of readmissions during of follow-up period. I will get the data in Hospital Admissions Service.

Institutionalization: Number of patients referred to nursing home after discharge or at any time during follow-up. This information is obtained directly from patients or their relatives.

Requirement of caregiver: Number of patients who require a caregiver after hospital discharge.

Caregiver burden: Will be used Zarit Scale for assessing caregiver burden

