9.3 EVALUATION AT 3 MONTHS OF DISCHARGE

Re-evaluate the following aspects by phone :

- Mortality
- Functionality data (Barthel index , Lawton index , PASE Scale).
- Usual medication.
- Residency at the moment.
- Frailty with the FRAIL scale..
- Data of quality of life with the scale EuroQolfive-dimensional (EQ-5D)
- Number of hospitalization and ER, indicate the cause (diagnosis)
- Caregiver burden with the economic questionaries .
- Economics evaluation, Index 3

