10 ECONOMIC EVALUATION

An economical evaluation of the program will be conducted to detect and handle the frail elderly in different health areas. We will conduct a comparative analysis in terms of costs and benefits of a geriatrician's intervention compared with usual care.

Information on both patients and caregivers about health resources and social services use and time spent by the caregiver will be collected. The next step is to translate this resource consumption in monetary terms. The costs will be reported in euros and in places where it is not used this coin the current exchange will take place.

The total cost is the sum of three different types of costs: directly deriveate from care; formal care costs (professional) and informal care costs (family and friends)

Direct health care costs:

These costs are related to inpatient treatment, outpatient treatment, medicines, etc. These are estimated from the use of health services by assigning a monetary value for each resource used.

Health resources will be identified and measured through questionnaires. Each center will give us the price or the monetary value of each resource. If some of this information is not available, it will be obtained from a systematic review of studies of cost of illness for each country.

Formal care costs (Social Services):

Formal care includes those generated by social services which can be public or privately funded institutions such as day care centers, remote assistance, scheduled home care, etc. These costs will be identified, measured and evaluated through questionnaires. Ideally, members of each research team from each center must provide to the economic team price and monetary values (unit costs) of resources for social services.

If data about unit cost of social services are not available, a review of the literature will be performed to obtain the data by country.

Social costs (informal care)

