Detach the next page along the lengthwise perforation, and then tear it in half along the horizontal perforation. Use the upper half of the page (blank) for the Comprehension, Writing, and Drawing items that follow. Use the lower half of the page as a stimulus form for the Reading ("CLOSE YOUR EYES") and Drawing (intersecting pentagons) items.

COMPREHENSION

Listen carefully because I am going to ask you to do something.

Take this paper in your right hand [pause], fold it in half [pause], and put it on the floor (or table).

TAKE IN RIGHT HAND _____ 0 1
FOLD IN HALF _____ 0 1
PUT ON FLOOR (or TABLE) _____ 0 1

READING

Please read this and do what it says. [Show examinee the words on the stimulus form.]

CLOSE YOUR EYES _____ 0 1

WRITING

Please write a sentence. [If examinee does not respond, say: Write about the weather.]

0 1

Place the blank piece of paper (unfolded) in front of the examinee and provide a pen or pencil. Score 1 point if the sentence is comprehensible and contains a subject and a verb. Ignore errors in grammar or spelling.

DRAWING

Please copy this design. [Display the intersecting pentagons on the stimulus form.]

0 1

[figure not shown]
Score 1 point if the drawing consists of two 5-sided figures that intersect to form a 4-sided figure.

Assessment of level of consciousness.

Total Score =
(Sum all item scores.) _____
(30 points max.)

Alert/ Responsive	Drowsy	Stuporous	Comatose/ Unresponsive

CLOSE YOUR EYES

ANEXO 3

Patient's information obtained from his/her clinical record

(Baseline)

1. **Patient's ID:** _____
2. (Register the generic names and total daily dose of drugs that the patient has taken during the last month)

		
		

3. 3. Hospitalization

What was the main cause of hospitalization?

	Diagnosis related Code Group (GRD)	GRD description	Mean stay (days)
			

Questionnaire for the subject(baseline)

1. **Identification number** _____

2. **Level of studies completed**

- Can read and write
- Primary
- Secondary
- University
- None

3. **Is the place where you live of your property?**

- Yes
- No

4. **Number of household members where the subject lives:** _____

people

5. **Carer**

a. **Do you need a carer to assist you with your daily activities?** (for basic hygiene, to help you to move, administration of drugs, performing treatments, etc. Monitoring and supervision tasks are also included)

- Yes
- No ⇒ Skip to question #6

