b. **In the case of yes, who is your principal carer?**

- Family member ⇒ Fill in the carer questionnaire and skip to question #6
- Another non-contracted person (friend) ⇒ Fill in the carer questionnaire and skip to question #6
- Professional carer (contracted or provided by an entity)

c. **If you use the services of a professional carer,**

How many hours a week? _____ hours a week

Who pays for the service and how much?

- I pay the entire cost of _____ € per hour

(Alternative, if the subject does not know the cost per hour)

- I pay the entire cost of _____ € per month
- The cost is covered by social security or another entity
- The cost is partially covered by social security or another entity, I pay _____ € per hour

(Alternative, if the subject does not know the cost per hour)

- The cost is partially covered by social security or another entity, I pay _____ € per month

6. Hospitalisation

Have you been admitted to hospital in the last 12 months?

- Yes
- No

7. Health and social services you have required and days of service received by according to economic system during the last month and the last 6 months.

Mark the services you have required, number of days received and form of payment. In case you have required a service and have not received it, note the reason number (see the possible reasons below the table).

Kinds of services	You have needed to receive..	Days service received according to economic system			Reason for which they have not received the service (*)
		Free of charge	Direct payment	Mixed (public and private)	
During the last month...		During the last month...			
1. Telecare		— days	— days	— days	

2. Domiciliary care /help		— days	— days	— days	
3. Day centre		— days	— days	— days	
4. Occupational centre or centre for cultural, recreational and leisure activities		— days	— days	— days	
5. Other:		— days	— days	— days	
In the last 6 months...		In the last 6 months...			
6. Respite services: Temporary stays		— days	— days	— days	
7. Residential centres		— days	— days	— days	
8. Other:		— days	— days	— days	

(*) Reasons: 1 – Waiting list. 2 – Not available in the setting. 3 – Cannot pay it. 4 – Does not comply with any of the requirements. 5 – Other reasons.

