On helping them to contact health care suppliers	hours	minutes	a week
On helping them to organise home adaptations	hours	minutes	a week
On shopping	hours	minutes	a week
On financial, administrative or legal affairs	hours	minutes	a week
On social and leisure activities	hours	minutes	a week
Monitoring and supervision (falls)	hours	minutes	a week

QUESTIONNAIRE FOR THE CARER (week 12)

The subject's principal informal carer (NOT CONTRACTED) fills in the questionnaire

****If it is the first contact that the care has with the study because the person that she/he looks after did not need a carer before or it is a different carer, the carer must fill the baseline's questionnaire.***

1. Identification number_____

HEALTH RELATED PROBLEMS

2. Have you had any health-related problem for caring the subject in the last 3 months?

- YES
- NO → skip to question #4

3. In case of YES, please specify this(multiple choice option)::

- I am depressed
- I am in treatment because of caregiving
- I am extremely tired
- I have back pain

WORK-RELATED PROBLEM

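### Annex 3 has no follow-up version of the subject questionnaire, so paid care and social-service use after randomisation have no specified instrument

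*Combined protocol and SAP*

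**What the plan says.** Section 10 divides total cost into direct health care, formal care (social services) and informal care. On formal care it states: "These costs will be identified, measured and evaluated through questionnaires". It then sets three perspectives: health care financing (direct health costs only), formal care financing (health plus social services) and society (all three).

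Section 4.2 defines the caregiver outcome as "Number of patients who require a caregiver after hospital discharge".

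Sections 9.2, 9.3 and 9.4 each call for the economic evaluation; the 3-month entry reads "Economics evaluation, Index 3". I take Index 3 to be Annex 3. Table 2 marks this row at discharge, 3 and 12 months and leaves the initial visit blank.

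Annex 3 prints five forms:

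- a clinical-record form, marked baseline;
- a subject questionnaire, headed "Questionnaire for the subject(baseline";
- carer questionnaires for first contact (baseline), week 12 and week 52.

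On the subject questionnaire, question 5a asks "Do you need a carer to assist you with your daily activities", question 5c asks about professional-carer hours and payment, and question 7 covers "Health and social services you have required and days of service received by according to economic system during the last month", with a 6-month look-back for some items. The week-12 and week-52 forms carry the instruction "The subject's principal informal carer (NOT CONTRACTED) fills in the questionnaire".

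**The concern.** Formal care cost and the requirement for a caregiver are both quantities that arise after discharge, yet the only items that measure them sit on a form labelled for use before any effect of the intervention could appear. The schedule says the reverse: economic evaluation at three later visits and none at baseline. A site that follows the form labels would not ask patients about paid care or services after randomisation. A site that follows the schedule would have to decide which form to use and over what recall period, and centres in three countries could decide differently.

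At stake are two of the three cost perspectives and the part of the caregiver outcome that concerns professional carers. Service use that is not asked about in the follow-up calls would be hard to recover afterwards.

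**Working it through.** The plan gives no figure to reproduce. The check sets the forms against the schedule and then works out what re-use of the baseline form would observe.

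**Step 1. Which forms exist after baseline (Annex 3).**

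- Patient forms: 2 printed, 0 with a follow-up version.
- Carer forms: 3 printed, 2 of them for follow-up (weeks 12 and 52).
- Economic evaluation in Table 2: 3 post-baseline visits, 0 baseline visits.

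**Step 2. Where each quantity is asked after randomisation.**

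| Quantity | Follow-up source |
|---|---|
| Telecare, home help, day-centre days | None |
| Professional-carer hours and payment | None |
| Need for a carer, as a direct question to the patient | None |
| New informal carer | Week-12 and week-52 notes: a new carer completes the baseline carer form |
| Residential care | Residence at 3 and 12 months, discharge destination, institutionalization: status, not days or payment |
| Informal-care hours | Week-12 and week-52 carer forms |
| Outpatient visits | None; 9.3 and 9.4 list hospitalizations and emergency visits |

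The follow-up carer forms ask about the unpaid carer's own problems and about unpaid time, not about purchased or provided services. Question 5b, which sends an informal carer to the carer form, is also printed only at baseline.

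**Step 3. What re-use of the baseline form would observe.** Assumptions: the form is repeated unchanged at 3 and 12 months after discharge (9.3, 9.4), and the target period is the 12 months after discharge (9.5). Use at discharge would look back only before discharge and adds nothing to this period.

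- 1-month items of question 7 (telecare, domiciliary care, day centre, occupational centre): months 2–3 and 11–12, so 1 + 1 = 2 months; 2/12 = 17%.
- 6-month items (respite stays, residential centres): the 3-month call covers months 0–3 after discharge plus about 3 months before it; the 12-month call covers months 6–12. Total 3 + 6 = 9 months; 9/12 = 75%, with months 3–6 not observed.
- Questions 5a and 5c have no look-back period and would give the situation at the two calls only.

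**Step 4. Recall on the week-52 carer form (a side point).** The form asks about problems in the last 6 months, taken as 26 weeks. Weeks since the week-12 contact: 52 − 12 = 40. Not asked about: 40 − 26 = 14 weeks, or 14/52 = 27% of the year. This applies to the questions on the carer's health, work and leisure problems. The hours questions refer to a normal day or week and have no such window.

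**The case against.** The strongest reply is that calling for Index 3 at discharge, 3 and 12 months already implies repeating the subject questionnaire, so the label is an editorial slip. That reading is possible, and it means the documents do not prove that the data will go uncollected. It does not settle the matter. Annex 3 prints separate carer forms for weeks 12 and 52 with their own recall periods, and nothing comparable for the patient. Step 3 shows that plain re-use would still leave most of the year unobserved for the 1-month items.

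A reader might infer three stronger things that the documents do not support.

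- That these quantities cannot be measured at all, or that the expected between-arm difference in formal care cost is zero. This holds only if the baseline form is the sole source, and the schedule points the other way. Residential care and new informal carers are also partly captured elsewhere.
- That drug costs are lost because the item "Register the generic names and total daily dose of drugs that the patient has taken during the last month" is on a baseline form. Medication is recorded at discharge, 3 and 12 months; only the dose is unstated. Polypharmacy is a count of drugs and does not need dose.
- That the 14-week carer recall gap weakens the cost analysis. Section 10 values informal care from time spent, and does not list carer leave or lost work as a cost.

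**Conclusion.** The point holds as a conflict between the Annex 3 labels and the schedule in sections 9.2 to 9.4 and Table 2, with a real gap on either reading. Read by the labels, telecare, home help, day-centre and paid-carer use have no post-randomisation instrument, and two of three cost perspectives lack an input. Read by the schedule, an unchanged form would observe about 2 of 12 months for the 1-month items and 9 of 12 for the 6-month items, so the rest would have to be extrapolated by a rule that the plan does not give. For the caregiver outcome, the gap is limited to newly needed paid carers and unmet need.

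The coverage figures assume contacts at 3 and 12 months, as sections 9.3 to 9.5 and Table 2 state; section 7.2 speaks of the third and sixth month. The affected outcomes are secondary, so this should be corrected but does not threaten the primary comparison.

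**What to change.** 1. In Annex 3, label the subject questionnaire for baseline, 3 months and 12 months. Keep the present look-back at baseline.
2. Ask questions 5 and 7 in the section 9.3 and 9.4 calls with recall since the last contact (since discharge at 3 months, since the 3-month call at 12 months). Repeating question 5b also restores the routing to the carer form.
3. Count the requirement of a caregiver from question 5, whether informal or professional, and report baseline carer status alongside. The section 4.2 definition itself need not change.
4. Add a count of outpatient visits, since section 10 names outpatient treatment as a direct cost.
5. Reconcile Table 2 and the discharge entry in 9.2 with the form labels: state which Annex 3 form is used at each visit, and mark the initial visit.
6. As a minor point, change the week-52 carer recall from 6 months to the period since the 3-month contact.

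Cost: existing questions and one new count in two calls that are already planned, at a few minutes each. Recall over nine months is less exact than over one or six, so some precision is traded for full coverage of the year.
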